**Table 7: Schedule of Assessments – Part 1, Cycle 2 (if Applicable) through Follow-up**

Dosing/Measurements/Evaluations	 Lu-DTPA-omburtamab Treatment Period  – Cycle 2		EOT and End of Trial
	Day 1 of cycle	Day 8 (±1), Day 15 (±1) of cycle	
Prior/concomitant medications	X	X	X
Physical examination 			
Vital signs 	X	X	X
Performance test 			X
MRI of the brain and spine 			X
Neurological examination 	X		X
Premedication (oral dexamethasone/IV equivalent) 	X		
Anti-pyretic and anti-histaminergic premedication 	X		
ICV  Lu-DTPA-omburtamab treatment dose	X		
Clinical chemistry and hematology 	X	X	X
CSF for cytology  , total protein, glucose, and cell count			X
Blood and CSF for culture	X 		
Blood and CSF sampling for ADA	X 		X
Blood and CSF sampling for pharmacokinetics	X 	X 	
Pregnancy testing 	X		X
Adverse events 	X	X	X

Abbreviations: ADA = anti-drug antibody; AE = adverse event; CSF = cerebrospinal fluid; ctDNA = circulating tumor deoxyribonucleic acid; EOT = end of treatment; HSA = human serum albumin; ICF = informed consent form; ICV = intracerebroventricular; IMP = investigational medicinal product; IV = intravenous; MRI = magnetic resonance imaging; NCI = National Cancer Institute; SAE = serious adverse event.

 The Lu-DTPA-omburtamab Treatment Period is divided into 5-week cycles. In Part 1, the patient can receive up to 2 cycles at the discretion of the investigator. Cycle 2 will start 35 days (adjustments to the dosing schedule will be accommodated on a patient-by-patient basis depending on the clinical condition of the patient.) after the first dose (dosimetry dose) of Cycle 1 and will consist of a treatment dose only (i.e., no dosimetry dose), on Day 1 of the cycle. The infusion reservoir must be flushed with HSA and CSF after each infusion.

 If the IMP is discontinued after Cycle 1, the Cycle 2 visits should be skipped, and after the EOT Visit should be done.

 Physical examinations to be performed as clinically indicated.

 Measurements of heart rate, respiratory rate, temperature, and blood pressure. On dosing day, measurements to be taken before and 30 min after the end of the IMP infusion.

 Lansky Scale <16 years, Karnofsky Scale ≥16 years.

 MRI of the brain and spine will be completed before first IMP administration, at the EOT Visit (preferably ±4 days of the actual visit date). MRI can be performed on a separate day to the other visit assessments, if required, in accordance with investigational site standards.

 Will be used to evaluate safety and efficacy.

 Beginning 24 hours before Lu-DTPA-omburtamab administration, divided into twice-daily doses for a total of 3 days.

 Given 1-2 hours prior to Lu-DTPA-omburtamab administration, including oral acetaminophen/paracetamol and antihistamine (e.g., diphenhydramine).

 In accordance with [Appendix 1](#).

 If CSF cytology sample is positive, it must be repeated within 4 weeks of the positive sampling.

 Drawn and held for culture only if elevated body temperature after dosing suggests infection rather than expected response to ICV dosing. Samples to be taken within 6 hours after completion of Lu-DTPA-omburtamab infusion.

 The ADA samples must be drawn prior to the Cycle 2 dose. The analysis can be performed from the samples drawn with the purpose of PK.

 Blood and CSF samples for pharmacokinetics will be drawn as per [Table 5](#). On Day 8, blood collection only.

 Pregnancy testing (serum or urine) is mandatory for women of childbearing potential at screening, within one week prior to each dose, and at the EOT Visit.

 Non-serious AEs should be reported from the day of first IMP administration until 5 weeks after the patient's last dose of IMP. Non-serious AEs occurring between signing the ICF and the first IMP administration must be recorded as medical history. Serious AEs should be reported from signing the ICF until 5 weeks after the patient's last dose of IMP.

Thereafter and during the follow-up period, only SAEs or Grade 3 or higher AEs at least possibly related to Lu-DTPA-omburtamab or to the presence of the indwelling catheter system should be reported until end of trial. During the post-trial monitoring period, new onset of cancers, regardless of causality, should be reported.

**Table 8: Schedule of Assessments – Part 2 (All Cycles)**

Dosing/Measurements/Evaluations	Screening	 Lu-DTPA-omburtamab Treatment Period 			EOT	Follow-up 	
		Cycles 1 through 5					
	Day -29* to -1	Day 1 of cycle	Day 15 (±1) of cycle	End-of-Cycle Visit (Day 29 [±1] of cycle)	5 to 6 weeks after last dose	26, 39, and 52 (±2) weeks post first dose	78 and 104 (±2) weeks post first dose
Informed consent 	X						
Eligibility check	X						
Demographics, height, body weight	X						
Medical, surgical, and disease history	X						
Prior/concomitant medications	X	X	X	X	X	X 	X 
Physical examination 	X						
Vital signs 	X	X	X	X	X	X	X
Performance test 	X 				X	X 	X 
MRI of the brain and spine 	X 			X 	X	X	X
Neurological examination 	X	X		X	X	X	X
Placement of an indwelling ICV access device	X 						
ICV access device patency/CSF flow assessment	X						
Premedication (oral dexamethasone/IV equivalent) 		X					
Anti-pyretic and anti-histaminergic premedication 		X					
ICV  Lu-DTPA-omburtamab treatment dose 		X					
Clinical chemistry and hematology 	X	X	X	X	X	X	
CSF for cytology  , total protein, glucose, and cell count	X 			X 	X	X	X
Blood and CSF for culture		X 					
Blood and CSF sampling for ADA	X 	X 			X		
Blood and CSF sampling for pharmacokinetics		X 					
Pregnancy testing 	X	X		X	X		
Adverse events 	X	X	X	X	X	X	X

Abbreviations: ADA = anti-drug antibody; AE = adverse event; CSF = cerebrospinal fluid; ctDNA = circulating tumor deoxyribonucleic acid; EOT = end of treatment; HSA = human serum albumin; ICF = informed consent form; ICV = intracerebroventricular; IMP = investigational medicinal product; IV = intravenous; MRI = magnetic resonance imaging; NCI = National Cancer Institute; SAE = serious adverse event.

\* A longer screening period (e.g., due to logistics, COVID-19 situations etc.) are allowed; however, eligibility evaluation must be re-confirmed. Screening period of >60 days with individual patient considerations to be discussed with the sponsor.

 The Lu-DTPA-omburtamab Treatment Period is divided into 5-week cycles. In Part 2, a cycle consists of a treatment dose on Day 1. The patient can receive up to 5 cycles at the discretion of the investigator. The infusion reservoir must be flushed with HSA and CSF after each infusion. The patient will be observed post treatment to decide if further cycles can be administered.

Day 1, 15, and 29 for Cycles 2 to 5 correspond to Day 36, 50, and 64 (for Cycle 2), Day 71, 85, 99 (for Cycle 3), 106, 120, 134 (for Cycle 4), and 141, 155, and 169 (for Cycle 5). Adjustments to the dosing schedule will be accommodated on a patient-by-patient basis depending on the clinical condition of the patient.

 If the IMP is discontinued prior to completion of all scheduled visits of the cycle (i.e., up to and including Day 29), the treatment visits that fall after the date of the EOT Visit should be skipped, and the patient should move directly into the follow-up phase. If the IMP is discontinued after Cycle 1, an unscheduled visit (including MRI etc.) should be done at 13 weeks post first dose.

 All patients who are dosed with Lu-DTPA-omburtamab in Part 2 should be followed up regularly (every 13 [±2] weeks, i.e., 26, 39, and 52 weeks post first dose, then every 26 [±2] weeks, i.e., 78 and 104 weeks post first dose, and thereafter annually) for monitoring of secondary malignancies during the trial and for at least 10 years after the end of trial, or until death, if sooner.

 Informed consent must be obtained before any trial-related procedures. If the indwelling ICV access device (e.g., Ommaya) is placed in connection with the tumor resection, the informed consent must be obtained prior to the surgery, and before the start of the screening period, unless this is placed as part of a standard of care procedure at site. If any procedures/tests are from before informed consent is obtained, it must be clear from source documents that this was not performed for the purpose of the present trial. In these cases, the procedures/tests do not need to be repeated at the Screening Visit if they were performed within the allowed timelines. The investigator is responsible for documenting this properly.

 Only anti-cancer therapy.

 Physical examinations to be performed at screening and as clinically indicated.

 Measurements of heart rate, respiratory rate, temperature, and blood pressure. On dosing days, measurements to be taken before and 30 min after the end of the IMP infusion.

 Lansky Scale <16 years, Karnofsky Scale ≥16 years.

 To be performed within 3 weeks prior to first IMP infusion. May be performed on the first dosing day but it must be before IMP administration.

 MRI of the brain and spine will be completed before first IMP administration and at the End-of-Cycle (Day 29) Visit for Cycles 1 and 3 only (±4 days of the actual visit date), EOT Visit (preferably ±4 days of the actual visit date), and each Follow-up Visit (±2 weeks of the actual visit date). MRI can be performed on a different day to the other visit assessments, in accordance with investigational site standards.

 Will be used to evaluate safety and efficacy.

 Beginning 24 hours before Lu-DTPA-omburtamab administration, divided into twice-daily doses for a total of 3 days.

 Given 1-2 hours prior to Lu-DTPA-omburtamab administration, including oral acetaminophen/paracetamol and antihistamine (e.g., diphenhydramine).

 In accordance with [Appendix 1](#) and until the first follow-up visit.

 If CSF cytology sample is positive, it must be repeated within 4 weeks of the positive sampling.

 Cycles 1 and 3 only.

 Drawn and held for culture only if elevated body temperature after dosing suggests infection rather than expected response to ICV dosing. Samples to be taken within 6 hours after completion of Lu-DTPA-omburtamab infusion.

 The ADA samples must be drawn prior to dosing. Serum and CSF samples for ADA analyses will be drawn at baseline, at the start of Cycle 2 (predose), and after last treatment. Presence of ADA will be analyzed at a central laboratory.

 Blood and CSF samples for pharmacokinetics will be drawn in Cycles 1 and 2 only, as per [Table 5](#).

 Pregnancy testing (serum or urine) is mandatory for women of childbearing potential at screening, prior to each dose, and at the EOT Visit.

 Non-serious AEs should be reported from the day of first IMP administration until 5 weeks after the patient's last dose of IMP. Non-serious AEs occurring between signing the ICF and the first IMP administration must be recorded as medical history. Serious AEs should be reported from signing the ICF until 5 weeks after the patient's last dose of IMP. Thereafter and during the follow-up period, only SAEs and Grade 3 or higher AEs at least related to Lu-DTPA-omburtamab or to the presence of the indwelling catheter system, should be reported. In the post-trial monitoring period, new onset of cancers, regardless of causality, should be reported.

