### 2.2.2.2. *Part 2*

- PK profile of Lu-DTPA-omburtamab in blood and CSF.
- Response, as defined by the RAPNO criteria (as determined from MRI assessments, neurological examination, and CSF cytology).
  - ORR, calculated as the proportion of all evaluable patients achieving a response (PR or CR) as best overall response at end of Cycle 1 and Cycle 3, EOT Visit, and at each Follow-up Visit.
- Investigator-assessed DoR, defined as the time from first response (CR or PR) to progression.
- PFS, defined as the time from first treatment to date of leptomeningeal progression or death from any cause, whichever comes first.
- OS defined as the time from first treatment to date of death.

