## 6. CONCOMITANT THERAPIES

Any medication or vaccine (including over-the-counter or prescription medicines, vitamins, and/or herbal supplements) that the patient is receiving at the time of enrolment or receives during the trial must be entered on the eCRF, including:

- reason for use
- dates of administration, including start and end dates, and
- dosage information including dose and frequency.

Prior anti-cancer therapy must be entered in the eCRF. The Medical Monitor should be contacted if there are any questions regarding concomitant or prior therapy.

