### 7.3.2. Response Evaluation, Overall Response Rate, and Duration of Response

Response, as defined by the RAPNO criteria (Warren et al. 2018; see Appendix 6) will be assessed in Part 1 at the EOT Visit. In Part 2, response will be assessed at end of Cycle 1 and Cycle 3, EOT Visit, then 26, 39, and 52 weeks post first dose, followed by 78 and 104 weeks post first dose of Lu-DTPA-omburtamab. Notably, objective response and stable disease requires that all criteria are met, while progression is defined when any of the PD criteria are met.

The ORR will be calculated from baseline MRI scans and from scans after the dosing of Lu-DTPA-omburtamab using 2 methods: firstly, by considering MRI data, neurological examination, and CSF cytology data together (RAPNO criteria); secondly, by considering CSF cytology data only. ORR will be defined as the proportion of all evaluable patients achieving a CR or PR as best overall response at the time of assessment.

Investigator-assessed DoR (Part 2) is defined as the time from response (CR or PR) to progression. Patients without any sign of progression will be censored at the date of their last PFS assessment.

In Part 1 and Part 2, the baseline CSF cytology assessment must be completed within 3 weeks prior to the first Lu-DTPA-omburtamab treatment dose infusion. Cerebrospinal fluid cytology should be assessed as positive/negative. Cerebrospinal fluid cytology will be assessed in Part 1 at screening, the EOT Visit, and in Part 2 at screening, end of Cycle 1 and Cycle 3, EOT Visit, and at each Follow-up Visit.

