### **8.4.1. Part 2 Efficacy Analysis**

Overall survival at 1 and 2 years post first dose will also be estimated using Kaplan-Meier methods. Patients not deceased will be censored at the last date known to be alive. The median PFS time and the proportion of patients without PFS events at 1 and 2 years post first dose will be estimated using Kaplan-Meier methods, along with their 95% confidence intervals. Results will be displayed in Kaplan-Meier plots. The ORR according to RAPNO criteria (MRI, neurological examination, and CSF cytology), as well as according to CSF cytology alone, will be assessed. The 95% confidence intervals will be calculated using the Clopper-Pearson exact methodology. Investigator-assessed DoR will be estimated using Kaplan-Meier methods. The median DoR and corresponding 95% confidence interval will be calculated.

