Steroid use	Off steroids or physiologic replacement doses only	Stable or less than baseline dose	Stable or less than baseline dose	
Extra-CNS disease	If positive at any timepoint, must be re-evaluated and have no evidence of disease	No new sites of disease	No new sites of disease	New sites of disease
Serum or CSF AFP, βhCG (if obtained, eg, germ cell tumors)	Must be within normal range for age			A previously negative (normal) assessment becomes positive

Abbreviations: βhCG=beta human chorionic gonadotropin; AFP=alpha-fetoprotein; CNS=central nervous system; CSF=cerebrospinal fluid; MRI=magnetic resonance imaging.

a If it is unclear that the patient has disease progression, it may be a reasonable option to keep the patient on study until subsequent assessments (e.g., MRI, CSF cytology) confirm progression. If subsequent testing confirms progression, the date of progression should be backdated to the onset of neurologic deterioration.

Adapted from Warren et al. 2018. Available at: <https://www.ncbi.nlm.nih.gov/pmc/articles/PMC5761545/>

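### Part 2 ORR: responses first seen or confirmed after the EOT Visit cannot be checked against the mandatory steroid criterion from the medication data that Table 8 schedules

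*Combined protocol and SAP*

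**What the plan says.** **Definition of response.** Section 7.3.2 defines response by the RAPNO criteria in Appendix 6 and adds that "objective response and stable disease requires that all criteria are met". The steroid row of Appendix 6 reads "Off steroids or physiologic replacement doses only" for CR and "Stable or less than baseline dose" for both PR and stable disease. Its cell for progressive disease is empty.

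**Derivation of the ORR.** Section 7.3.2 then describes two calculations, the first being "firstly, by considering MRI data, neurological examination, and CSF cytology data together (RAPNO criteria"; the second uses cytology only. Section 8.4.1 words the first as "The ORR according to RAPNO criteria (MRI, neurological examination, and CSF cytology". Section 2.2.2.2 and the Synopsis list the same three inputs. None of these places mentions steroids.

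**When response is assessed.** Section 2.2.2.2 takes the ORR at the ends of Cycles 1 and 3, "EOT Visit, and at each Follow-up Visit". Section 7.3.2 gives the follow-up times as weeks 26, 39, 52, 78 and 104.

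**What medication is recorded.** Table 8 asks for concomitant medication without restriction from Screening through EOT. At the five Follow-up Visits, footnote 5 limits it to "Only anti-cancer therapy". Section 6, in contrast, says that any medication the patient "receives during the trial must be entered on the eCRF", with dates, dose and frequency.

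**The concern.** The plan sets a condition for response, leaves it out of the text from which the ORR would be programmed, and at follow-up does not schedule the data needed to apply it. A site that works from Table 8 will leave a corticosteroid course off the eCRF after EOT, while one that works from Section 6 will enter it. The same patient could then be checkable at one site and not at another.

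The rest of the plan does not close the gap. Exclusion criterion 6 in Section 4.2 leaves corticosteroids out of its washout, Section 6.2 does not prohibit them, and Section 6.1 allows supportive treatment after EOT. Adverse event reporting in follow-up is also narrowed (Section 7.4.5), essentially to events related to the product or the catheter and to new cancers. A steroid started for some other symptom need not leave a trace there either.

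At stake is whether a late CR or PR that enters the ORR can be shown to meet the plan's own definition. Doses not recorded at the time may be hard to recover later.

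**Working it through.** **1. The plan's own figure.** Section 8.1 assumes 20 evaluable patients and 5 responders, and states a 95% lower limit of 9%. Section 8.4.1 names Clopper-Pearson. For x responders in n:

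- lower limit = Beta quantile (0.025; x, n − x + 1)
- upper limit = Beta quantile (0.975; x + 1, n − x)

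With x = 5 and n = 20, the lower limit is Beta quantile (0.025; 5, 16) = 8.66%, which rounds to 9%. The figure reproduces.

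**2. Which responses are exposed.** Appendix 6 requires an MRI response to hold for 4 weeks or more. Times below are weeks after first dose, (day − 1)/7, using the Part 2 days in Table 8 footnote 1 and the EOT Visit five to six weeks after last dosing.

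- End of Cycle 1: Day 29, 28/7 = week 4.
- End of Cycle 3: Day 99, 98/7 = week 14.
- EOT after five cycles: last dose Day 141, so Day 176 to 183, or 175/7 to 182/7 = weeks 25 to 26.

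For a patient who has all five cycles on schedule:

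| Response first seen | Next scheduled scan at least 4 weeks later (nominal) | Medication recorded there |
|---|---|---|
| End of Cycle 1 (week 4) | End of Cycle 3, 10 weeks later | All |
| End of Cycle 3 (week 14) | EOT, 11 to 12 weeks later | All |
| EOT (weeks 25 to 26) | Week 39, 13 to 14 weeks later (nominal week 26 is only 0 to 1 week later) | Anti-cancer therapy only |
| Any Follow-up Visit | A later Follow-up Visit | Anti-cancer therapy only |

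The first two rows are verifiable from scheduled data. The last two are not.

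Patients who stop early reach follow-up sooner. After one cycle, EOT falls on Day 36 to 43 (weeks 5 to 6), which is 1 to 2 weeks after the Cycle 1 scan and too soon to confirm a response seen there. Footnote 2 adds a week 13 visit with MRI for these patients but does not say which medication rule applies.

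**3. Size.** No document gives a rate of response that fails only on steroids, so I assume a range: 0 to 2 of the 5 planned responders fail the steroid row, and all stay in the denominator. Each one moves the ORR by 1/20 = 5 points.

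| Failing the steroid row | ORR | Exact 95% interval |
|---|---|---|
| 0 | 5/20 = 25% | 8.7% to 49.1% |
| 1 | 4/20 = 20% | 5.7% to 43.7% |
| 2 | 3/20 = 15% | 3.2% to 37.9% |

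The same arithmetic would describe any misclassified responder at n = 20. It shows sensitivity and does not estimate an error rate.

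**4. Baseline dose.** The PR and stable disease cells compare with a baseline steroid dose that the plan does not define. Section 6.3 starts dexamethasone premedication a day before each infusion. Table 8 footnote 9 lets the baseline MRI take place on the first dosing day, when premedication has already begun. If baseline steroid use were read on that day, the premedication dose could become the reference and the criterion would be easier to meet later.

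**The case against.** The strongest reply is that the plan already requires the steroid condition. Section 7.3.2 sends the reader to Appendix 6 and insists on every criterion. The three inputs in parentheses serve to separate the composite ORR from the cytology-only one; the Appendix 6 row on disease outside the CNS is not named there either. This stands. A reader might infer that the ORR rests on three inputs by definition, so that a response reached on a raised steroid dose counts. The documents do not support that: such a patient does not meet CR or PR. The fault is a mismatch between the definition and both the derivation wording and the follow-up data capture.

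Second, Section 6 arguably requires the missing data. This also stands, so it cannot be said that steroid data will be absent at follow-up. The two instructions contradict each other, and the visit schedule is the one that drops the data.

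Third, response is assessed by the investigator, who can apply Appendix 6 from the clinical record. This is fair: an eCRF gap does not prove that the criterion goes unapplied. It does mean that its application cannot be checked from the scheduled data.

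Fourth, the five Follow-up Visits are five of the eight response times in Section 7.3.2, and a reader might infer that most of the ORR is affected. It is not. The ORR uses best overall response, recording is complete through EOT, and after five cycles on schedule EOT falls inside the week 26 ± 2 window.

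Fifth, a reader might infer that DoR is biased upward. DoR ends at progression and the steroid cell for progression is empty, so no direction can be claimed. Nor do the documents say how often these patients take steroids or what steroids do to their scans, and the point does not rely on either.

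**Conclusion.** The point holds in limited form. The steroid row is mandatory for CR, PR and stable disease. The ORR text does not name it, and footnote 5 conflicts with Section 6 on whether the data are collected after EOT. Late or late-confirmed responses are therefore unverifiable from the data that Table 8 schedules. For responses seen and confirmed by EOT, the data are there and only the derivation wording needs repair.

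If the omission has an effect, it is to overstate the ORR, because a dropped condition can only add responders. The size is unknown. The 25%, 20% and 15% scenarios rest on an assumed 0 to 2 failures among the 5 planned responders.

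ORR is a secondary, descriptive endpoint: no hypothesis test or decision threshold depends on it, and the Part 2 primary endpoint (TEAEs) is untouched. The change is still worth making, because a stated rule leaves a required criterion uncheckable and the remedy is cheap.

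**What to change.** 1. **Table 8 footnote 5 and Section 6.** Change the footnote to: *Anti-cancer therapy and corticosteroids only (drug, daily dose, dates).* Amend Section 6 to state the same limit for the follow-up period, so that the two agree. Say which rule applies at the week 13 visit in footnote 2.
2. **Sections 2.2.2.2, 7.3.2 and 8.4.1.** State that RAPNO response is derived from all applicable Appendix 6 rows, including steroid use. Align the Synopsis.
3. **Baseline.** Define the baseline steroid dose, for response purposes, as the dose before protocol dexamethasone premedication begins.
4. **Classification.** State how a visit that fails only the steroid row is handled, since the progressive disease cell is empty. One option is to call that visit not evaluable for response while keeping the patient in the ORR denominator.

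The cost is one eCRF item at five follow-up visits plus the wording changes. The reported ORR may come out slightly lower.
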